6.0 ADVERSE EVENTS: LIST AND REPORTING REQUIREMENTS

Adverse event (AE) monitoring and reporting is a routine part of every clinical trial. The following list of expected AEs (Section 6.1) and the characteristics of an observed AE (Section 6.2) will determine whether the event requires expedited (via CTEP-AERS) in addition to routine reporting (via AdvantageEDCSM).

CTCAE term (AE description) and grade: The descriptions and grading scales found in the revised NCI Common Terminology Criteria for Adverse Events (CTCAE) version 5.0 will be utilized for AE reporting beginning April 1, 2018. All appropriate treatment areas should have access to a copy of the CTCAE version 5.0. A copy of the CTCAE version 5.0 can be downloaded from the CTEP web site

http://ctep.cancer.gov/protocolDevelopment/electronic_applications/ctc.htm. This study will be monitored by the Clinical Data Update System (CDUS). Cumulative CDUS data will be submitted quarterly to CTEP by electronic means. Reports are due January 31, April 30, July 31, and October 31.

A monthly conference call between all participating institutions will be conducted to discuss all adverse events encountered.

6.1 Comprehensive Adverse Events and Potential Risks Lists (CAEPRs) for Brentuximab Vedotin (SGN-35, NSC 749710)

The Comprehensive Adverse Events and Potential Risks list (CAEPR) provides a single list of reported and/or potential adverse events (AE) associated with an agent using a uniform presentation of events by body system. In addition to the comprehensive list, a subset, the Specific Protocol Exceptions to Expedited Reporting (SPEER), appears in a separate column and is identified with bold and italicized text. This subset of AEs (SPEER) is a list of events that are protocol specific exceptions to expedited reporting to NCI (except as noted below). Refer to the 'CTEP, NCI Guidelines: Adverse Event Reporting Requirements'

http://ctep.cancer.gov/protocolDevelopment/electronic_applications/docs/aeguidelines.pd f for further clarification. *Frequency is provided based on 798 patients*. Below is the CAEPR for SGN-35 (brentuximab vedotin).

NOTE: Report AEs on the SPEER ONLY IF they exceed the grade noted in parentheses next to the AE in the SPEER. If this CAEPR is part of a combination protocol using multiple investigational agents and has an AE listed on different SPEERs, use the lower of the grades to determine if expedited reporting is required.

Relatio	Specific Protocol Exceptions to Expedited Reporting (SPEER)		
Likely (>20%)	Less Likely (<=20%)	Rare but Serious (<3%)	
BLOOD AND LYMPHA	TIC SYSTEM DISORDERS	· · · · · · · · · · · · · · · · · · ·	
	Anemia		Anemia (Gr 2)
		Febrile neutropenia	
GASTROINTESTINAL	DISORDERS		
	Abdominal pain		
		Colitis ²	
	Constipation		Constipation (Gr 2)
Diarrhea			Diarrhea (Gr 2)
		Enterocolitis	
		Gastrointestinal hemorrhage ³	
		Gastrointestinal obstruction ⁴	
		Gastrointestinal perforation ⁵	
		Gastrointestinal ulcer ⁶	
		Ileus	
Nausea			Nausea (Gr 2)
		Pancreatitis	
	Vomiting		Vomiting (Gr 2)
GENERAL DISORDERS	S AND ADMINISTRATION S	ITE CONDITIONS	
	Chills		
	Edema limbs		
Fatigue			Fatigue (Gr 2)
	Fever		Fever (Gr 2)
	Pain		
HEPATOBILIARY DISC	DRDERS	1	
	Hepatobiliary disorders - Other (hepatotoxicity) ⁷		
IMMUNE SYSTEM DIS	ORDERS		
		Anaphylaxis	
INFECTIONS AND INF	ESTATIONS		
	Lung infection		
	Upper respiratory infection		Upper respiratory infection (Gr 2)
INJURY, POISONING A	ND PROCEDURAL COMPL	ICATIONS	
		Infusion related reaction	
INVESTIGATIONS			
	Alanine aminotransferase		
	increased		
	Aspartate aminotransferase increased		
Neutrophil count decreased			Neutrophil count decreased (Gr 4)
	Platelet count decreased		
	Weight loss		
	White blood cell decreased		
METABOLISM AND N	UTRITION DISORDERS		
	Anorexia		Anorexia (Gr 2)

Adverse Events with Possible Relationship to SGN-35 (brentuximab vedotin) (CTCAE 5.0 Term) [n= 798]			Specific Protocol Exceptions to Expedited Reporting (SPEER)
Likely (>20%)	Less Likely (<=20%)	Rare but Serious (<3%)	
	Hyperglycemia		
		Tumor lysis syndrome	
MUSCULOSKELETAL AND CONNECTIVE TISSUE DISORDERS			
	Arthralgia		Arthralgia (Gr 2)
	Back pain		
	Muscle cramp		
	Myalgia		Myalgia (Gr 2)
	Pain in extremity		
NERVOUS SYSTEM DI	SORDERS		
	Dizziness		
	Headache		Headache (Gr 2)
		Nervous system disorders - Other (progressive multifocal leukoencephalopathy)	
	Paresthesia		
	Peripheral motor neuropathy		Peripheral motor neuropathy (Gr 2)
Peripheral sensory neuropathy			Peripheral sensory neuropathy (Gr 2)
PSYCHIATRIC DISORDERS			
	Anxiety		
	Insomnia		
RESPIRATORY, THOR	ACIC AND MEDIASTINAL I	DISORDERS	
,	Cough		Cough (Gr 2)
	Dyspnea		
	Oropharyngeal pain		
		Respiratory, thoracic and mediastinal disorders - Other (pulmonary toxicity) ⁸	
SKIN AND SUBCUTAN	IEOUS TISSUE DISORDERS		
	Alopecia		Alopecia (Gr 2)
	Hyperhidrosis		
	Pruritus		Pruritus (Gr 2)
	Rash maculo-papular		Rash maculo-papular (Gr 2)
		Stevens-Johnson syndrome	
		Toxic epidermal necrolysis	

¹This table will be updated as the toxicity profile of the agent is revised. Updates will be distributed to all Principal Investigators at the time of revision. The current version can be obtained by contacting [contact]. Your name, the name of the investigator, the protocol and the agent should be included in the e-mail. ²Colitis may also include the term neutropenic colitis.

³Fatal and/or serious gastrointestinal hemorrhages have been observed in SGN-35 (brentuximab vedotin) treated patients. Gastrointestinal hemorrhage includes Anal hemorrhage, Cecal hemorrhage, Colonic hemorrhage, Duodenal hemorrhage, Esophageal hemorrhage, Esophageal varices hemorrhage, Gastric hemorrhage, Hemorrhoidal hemorrhage, Ileal hemorrhage, Intra-abdominal hemorrhage, Jejunal hemorrhage, Lower gastrointestinal hemorrhage, Oral hemorrhage, Pancreatic hemorrhage, Rectal hemorrhage, Retroperitoneal hemorrhage, and Upper gastrointestinal hemorrhage under the GASTROINTESTINAL DISORDERS SOC.

⁴Fatal and/or serious gastrointestinal obstructions have been observed in SGN-35 (brentuximab vedotin) treated patients. Gastrointestinal obstruction includes Colonic obstruction, Duodenal obstruction, Esophageal obstruction, Ileal obstruction, Jejunal obstruction, Obstruction gastric, Rectal obstruction, Small intestinal obstruction, and other sites under the GASTROINTESTINAL DISORDERS SOC.

⁵Fatal and/or serious gastrointestinal perforations have been observed in SGN-35 (brentuximab vedotin) treated patients. Gastrointestinal perforation includes Colonic perforation, Duodenal perforation, Esophageal perforation, Gastric perforation, Ileal perforation, Jejunal perforation, Rectal perforation, and Small intestinal perforation under the GASTROINTESTINAL DISORDERS SOC. Lymphoma with preexisting GI involvement may increase the risk of perforation.

⁶Fatal and/or serious gastrointestinal ulcers have been observed in SGN-35 (brentuximab vedotin) treated patients. Gastrointestinal ulcer includes Anal ulcer, Colonic ulcer, Duodenal ulcer, Esophageal ulcer, Gastric ulcer, Ileal ulcer, Jejunal ulcer, Rectal ulcer, and Small intestine ulcer under the GASTROINTESTINAL DISORDERS SOC. ⁷Hepatotoxicity may manifest as increased ALT/AST, bilirubin, alkaline phosphatase, and/or GGT.

⁸Pulmonary toxicity, which may manifest as pneumonitis, interstitial lung disease, or adult respiratory distress syndrome (ARDS), has been observed in patients treated in brentuximab vedotin monotherapy trials as well as in combination with bleomycin.

Adverse events reported on SGN-35 (brentuximab vedotin) trials, but for which there is insufficient evidence to suggest that there was a reasonable possibility that SGN-35 (brentuximab vedotin) caused the adverse event:

BLOOD AND LYMPHATIC SYSTEM DISORDERS - Blood and lymphatic system disorders - Other (lymphadenopathy)

CARDIAC DISORDERS - Myocardial infarction; Pericardial effusion; Sinus tachycardia

GASTROINTESTINAL DISORDERS - Dyspepsia; Esophagitis GENERAL DISORDERS AND ADMINISTRATION SITE CONDITIONS - Noncardiac chest pain

INFECTIONS AND INFESTATIONS - Meningitis; Pharyngitis; Sepsis; Shingles; Sinusitis; Skin infection; Soft tissue infection; Thrush; Urinary tract infection **INVESTIGATIONS** - Blood lactate dehydrogenase increased; Carbon monoxide diffusing capacity decreased; Creatinine increased; Lipase increased; Lymphocyte count decreased

METABOLISM AND NUTRITION DISORDERS - Dehydration; Hypercalcemia; Hyperkalemia; Hypertriglyceridemia; Hyperuricemia; Hypocalcemia; Hypoglycemia; Hypokalemia; Hypomagnesemia; Hypophosphatemia

MUSCULOSKELETAL AND CONNECTIVE TISSUE DISORDERS - Bone pain; Generalized muscle weakness; Myositis; Neck pain

NEOPLASMS BENIGN, MALIGNANT AND UNSPECIFIED (INCL CYSTS AND POLYPS) - Myelodysplastic syndrome

NERVOUS SYSTEM DISORDERS - Dysesthesia; Encephalopathy; Nervous system disorders - Other (demyelinating polyneuropathy); Seizure; Syncope

PSYCHIATRIC DISORDERS - Depression **RENAL AND URINARY DISORDERS** - Acute kidney ini

RENAL AND URINARY DISORDERS - Acute kidney injury; Renal and urinary disorders - Other (pyelonephritis)

REPRODUCTIVE SYSTEM AND BREAST DISORDERS - Irregular menstruation; Reproductive system and breast disorders - Other (groin pain)

RESPIRATORY, THORACIC AND MEDIASTINAL DISORDERS - Adult respiratory distress syndrome⁸; Pleural effusion⁸; Pneumothorax⁸; Productive cough; Respiratory failure; Respiratory, thoracic and mediastinal disorders - Other (bronchitis) **SKIN AND SUBCUTANEOUS TISSUE DISORDERS** - Dry skin **VASCULAR DISORDERS** - Hot flashes; Hypertension; Hypotension; Thromboembolic event

Note: SGN-35 (brentuximab vedotin) in combination with other agents could cause an exacerbation of any adverse event currently known to be caused by the other agent, or the combination may result in events never previously associated with either agent.

6.1.1 Special Precautions/Safety Issues

Infusion-Related Reactions

Some patients experienced an infusion-related reaction during or soon after SGN-35 treatment. Symptoms of infusion-related reactions included chills, nausea, cough, itching, and shortness of breath. Two patients experienced a serious allergic reaction (wheezing/difficulty breathing, hives, itching, swelling) that required immediate medical attention and treatment discontinuation.

Peripheral Neuropathy

Some patients who received SGN-35 developed peripheral neuropathy. Symptoms reported by these patients included burning sensation, pain, weakness, numbness and tingling of hands and/or feet, and severe abnormal nerve function that caused difficulty walking.

Neutropenia

Some patients experienced neutropenia that was related to treatment with SGN-35. This could result in an increased risk of infection.

Infection Risk

SGN-35 may cause patients to be less resistant to infections, including severe infections.

Other Important Side Effects

The following important or potentially life-threatening side effects have been reported infrequently in patients treated with SGN-35:

• Serious allergic reaction (wheezing/difficulty breathing, hives, itching, swelling) during or soon after SGN-35 treatment, which requires immediate medical attention and treatment discontinuation

- Severe leukopenia, fever, and possible infection that resulted in death
- Stevens-Johnson syndrome (unexplained widespread skin pain, blisters on skin and mucous membranes, hives, tongue swelling, a red or purple skin rash that spreads, or unexplained shedding of skin)
- Tumor lysis syndrome (TLS) is a potentially life-threatening complication. TLS usually occurs within a few days of the start of cancer treatment and may result in metabolic complications. Potential complications may include nausea, vomiting, edema (swelling), shortness of breath, heart rhythm disturbances, and acute renal failure.
- Progressive Multifocal Leukoencephalopathy (PML) is a rare, serious brain infection caused by a certain virus. People with a weakened immune system can experience PML. PML can result in death or severe disability. Care providers should be mindful of confusion or problems thinking, loss of balance or problems walking, difficulty speaking, decreased strength or weakness on one side of your body, blurred vision or loss of vision.

Pregnancy and Breastfeeding

Brentuximab vedotin is pregnancy category D; therefore, participants should not receive SGN-35 if they are pregnant because of the risk to the fetus. SGN-35 affects the testes in animals; therefore, men should not get their partner pregnant while being treated with SGN-35.

- Female study volunteers of reproductive potential (defined as girls who have reached menarche and pre-menopausal women who have not had a sterilization procedure such hysterectomy, bilateral oophorectomy, or salpingectomy) **must** have a negative serum or urine pregnancy test performed within 48 hours before initiating the protocol-specified medication(s). Women are considered menopausal if they have not had a menses for at least 12 months and have a FSH of greater than 40 IU/L or, if FSH testing is not available, they have had amenorrhea for 24 consecutive months.
- All study volunteers, male and female, must agree not to participate in a conception process (e.g., active attempt to become pregnant or to impregnate, sperm donation, or in vitro fertilization).
- If participating in sexual activity that could lead to pregnancy, **all** study volunteers must agree to use **two reliable methods of contraception simultaneously** while receiving protocol-specified medication(s) and for 6 months after stopping the medication(s).
- If the female volunteer is not of reproductive potential (defined above) or the man has documented azoospermia, contraception is not required.

Participants who could become pregnant or who have partners who could become pregnant must use birth control during the study and for 6 months after stopping treatment. If a participant or a participant's partner becomes pregnant while taking part in this study or within 6 months after stopping treatment, the participant should inform the study doctor right away. Seattle Genetics will follow the pregnancy to term. In addition, the resultant progeny will be followed for potential side effects for some period of time after birth.

It is not known whether SGN-35 or its breakdown products end up in breast milk. If it does end up in breast milk, it could cause harm to a nursing baby. Therefore, breast feeding is prohibited while on study drug and for 6 months after the last dose of study drug.

Possible Risks in Combination with Other Therapies

Concomitant use of SGN-35 and bleomycin is contraindicated due to pulmonary toxicity. In a clinical trial that studied SGN-35 with bleomycin as part of a combination regimen (ABVD), the rate of noninfectious pulmonary toxicity was higher than the historical incidence reported with ABVD. Monotherapy with SGN-35 has not been associated with a clinically meaningful risk of pulmonary toxicity.

An ongoing phase 1 study is investigating the combination of SGN-35 with ABVD or AVD as front-line therapy for HL. Noninfectious pulmonary toxicity was observed in some patients treated with SGN-35 in combination with ABVD. The incidence of pulmonary toxicity in the ABVD + SGN-35 arm of the trial was approximately 40% (10 of 25 patients), compared to an incidence of 10% to 25% most commonly reported in the literature with bleomycin-based regimens⁷⁹⁻⁸¹. Patients presented with cough and dyspnea. Interstitial infiltration and/or inflammation were observed on X-ray and computed tomography of the chest. Five patients had a maximum severity \geq Grade 3 (3 with Grade 3 and 2 with Grade 4). Most patients responded favorably to corticosteroid therapy.

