3.0 PARTICIPANT SELECTION

A rostered AMC investigator (CTEP-registered physician investigator) must document that each protocol participant meets all stated eligibility criteria. Participating sites must have documentation that each eligibility requirement is satisfied prior to participant enrollment. In compliance with CTEP policy, no exceptions to eligibility criteria will be granted under any circumstance.

NOTE: Institutions may use this section of the protocol as an eligibility checklist for source documentation if it has been reviewed, signed, and dated before registration/randomization by the study investigator. If used as source documentation, this checklist must be printed, the investigator must check each item to document their assessment that the participant meets each eligibility criterion, and the completed checklist must be maintained in the participant's chart. NOTE: All questions regarding eligibility should be directed to the study chair.

Participant ID Number: 085 - ____ - ___ - ____

Patient's Initials (L, F, M): _____

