- 3.1.9 Total bilirubin must be < 1.5 x the upper limit of normal, unless the elevation of bilirubin is thought to be secondary to Gilbert's syndrome or cART. If, however, the elevated bilirubin is felt to be secondary to antiretroviral therapy, the total bilirubin must be $\leq 3.5 \text{ mg/dL}$, provided that the direct bilirubin is normal and the AST and ALT $\leq 3 x$ the upper limit of normal. Also, if the elevated bilirubin is thought to be secondary to cHL the same criteria for hyperbilirubinemia should be applied; however 1 prior cycle of cyclophosphamide is permitted in attempt to make the participant eligible (see Section 3.1.5). Patients should not be excluded from study participation unless dosing cannot be safely established as per Section 5.2.5.
- 3.1.10 Female participants must have a negative pregnancy test within 1 week of enrollment and **all** participants must agree to **use two reliable methods of contraception simultaneously** if conception is possible during the study and for 6 months after stopping treatment. Should a woman participant become pregnant or suspect she is pregnant while the participant is participating in this study, she should inform her treating physician immediately. The participant will then be removed from protocol therapy. Participants who father a child while participating in the study will be permitted to continue with the protocol. The participant, however, is required to notify the investigator if he fathers a child.
- _____ 3.1.11 Ability to understand and the willingness to sign a written informed consent document.
- 3.1.12 Karnofsky performance status > 30% (given the aggressiveness of this disease and the often severely debilitated nature of the patients at initial presentation). See Appendix III.
- 3.1.13 Measurable or non-measurable (evaluable) tumor parameter(s). Non-measurable tumor parameters will be defined as not having bi-dimensional measurements (i.e., gastric or marrow involvement) but can be followed for response by other diagnostic tests such as gallium, PET imaging and/or bone marrow biopsy.
- _____ 3.1.14 Patients already receiving erythropoietin or GCSF for treatment of HIV-related cytopenia are eligible.
- 3.1.15 CD4 count \geq 50 cells/µL.

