3.5 Participant Enrollment Procedures

Sites must have this protocol approved by their Institutional Review Boards (IRB) and be registered for study participation with the AMC Operations and Data Management Center (ODMC) before they may enroll participants.

After it has been determined that the participant is eligible and an informed consent has been signed by the participant, the participant must be registered on-line via the AMC AdvantageEDCSM Internet Data Entry System (AdvantageEDC). Enrollment and data collection will occur via the AMC Internet Data Entry System.

The participating site will ensure a participant meets all eligibility criteria prior to completing the protocol-specific eligibility checklist in AdvantageEDC for enrollment. Participants will be enrolled on-line via AdvantageEDC no more than 1 week prior to the initiation of treatment (enrollment 1 day prior to or on the day of treatment is strongly encouraged). Once the eligibility checklist is submitted a system-generated confirmation email will be sent to the enroller upon successful completion of the participant enrollment. If the on-line system is inaccessible, the site should notify the AMC ODMC (via email at [contact] or via phone at [contact]) for further instructions.

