 - 8.1.12.4 HIV-1 RNA viral load to be assessed by any FDA-approved viral load assay (evaluated at the local laboratory). This must be performed within 21 days prior to Cycle 1, Day 1. (The HIV viral load assay must detect at minimum viremia > 200 copies/mL to be consistent with the DHHS HIV treatment guidelines).
 - 8.1.12.5 Assessment for Hepatitis C antibody, Hepatitis B core antibody, Hepatitis B surface antigen (HBsAg), and Hepatitis B surface antibody.
 - 8.1.12.6 Serum or urine pregnancy test for women of childbearing potential (within 7 days prior to Cycle 1 chemotherapy). (See Section 6.1.1 under pregnancy and breastfeeding for guidelines on the use of pregnancy category D medications, which includes brentuximab vedotin and dacarbazine.)

- 8.1.12.7 Blood samples to be taken for EBV tumor DNA studies. See Section 10.0 and Appendix XI for time points needed, sample processing, and shipping instructions. This will be done only in the Phase II portion of the study.
- 8.1.12.8 Blood samples to be taken for cytokine studies. See Section 10.0 and Appendix X for time points needed, sample processing, and shipping instructions. This will be done only in the Phase II portion of the study.
- 8.1.12.9 Blood samples will be taken for analysis of latent and HIV reservoirs. See Section 10.0 and Appendix XII for time points needed, sample processing, and shipping instructions. Only for participants who are found to have undetectable plasma HIV-1 RNA by the standard assay performed at the clinical site within 21 days of C1 Day 1.

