APPENDIX I: SCHEDULE OF EVALUATIONS

Evaluations	Eligibility (Baseline) ^a	Cycle 1-6 Day 1	Cycle 1-6 Day 15	Cycle 2 Day 1	Cycle 2 Day 22-28	Cycle 3 Day 1	Cycle 4 Day 1	Cycle 5 Day 1	Post- Treatment	Early Treatment Discontinuation ^j
Informed consent	Х									
ACSR consent and donation (optional)	Х									
Medical history and physical examination	Х	Xg							Xb	Х
FDG-PET/CT or FDG-PET + CT	Xº				Х				Xr	
CT scan with oral/IV contrast	X ⁿ								X ⁱ	
MRI of brain with and without IV gadolinium contrast	Х									
MUGA or echocardiogram	Х									
FACT-GOG-neurotoxicity questionnaire		X ^g								
Bone marrow biopsy	Xc								X ^d	
Central pathology review	Х									
Paraffin Cores for miRNA and Tissue Microarray Analysis	Х									
CBC with diff	Xe	X ^h	X ^h						X ^b	X
Sedimentation rate	Xe									
Serum chemistries: electrolytes (Na, K, Cl, bicarbonate, Ca, Mg, phosphorus), glucose, BUN, creatinine, total bilirubin, alkaline phosphatase (ALP), LDH, total protein, albumin, AST and ALT	X°	X ^g	X ^g						Xb	Х
CD4/CD8 cell count	Х			X ^g				X ^g	Xq	X ^k
HIV-1 RNA viral load	X ^p			Xg				Xg	Xq	X ^k
Hepatitis C antibody, Hepatitis B core antibody, Hepatitis B surface antigen (HBsAg), and Hepatitis B surface antibody	X									
Serum or urine pregnancy test	Xf									

Evaluations	Eligibility (Baseline) ^a	Cycle 1-6 Day 1	Cycle 1-6 Day 15	Cycle 2 Day 1	Cycle 2 Day 22-28	Cycle 3 Day 1	Cycle 4 Day 1	Cycle 5 Day 1	Post- Treatment	Early Treatment Discontinuation ^j
Pharmacokinetic studies (select Phase II participants only)		X^l	X^l						X^l	X^1
EBV/Immunogenicity Studies (Phase II only)	X ^m	X ^m							X ^m	X ^m
HIV Reservoir Studies	X ^s					Xt			X ^u	X^k

- A. Screening to be completed within 6 weeks prior to participant registration unless otherwise specified.
- B. Post-treatment evaluation to occur within 6-8 weeks of the last treatment dose and then every 3 months thereafter (+/- 7 days) for 2 years; every 6 (+/- 7 days) months for the third through fifth years unless otherwise specified.
- C. Does not have to be repeated if bone marrow involvement by lymphoma already documented after bone marrow biopsy more than 6 weeks prior to registration.
- D. Only need to perform to confirm CR is positive at baseline (only once, within 8 weeks of last treatment dose).
- E. Must be completed within 2 weeks prior to participant registration.
- F. To be performed within 7 days prior to Cycle 1, Day 1.

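### The pregnancy-test schedules are looser than the protocols' own 48-hour rule, and French section 14.1.1 pairs 6 months of contraception with a 30-day post-treatment notification clause

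*Combined protocol and SAP*

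**What the plan says.** **Test timing, both protocols.**

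- The rule is in AMC section 6.1.1 and, in the same words, French section 14.1.1. Women of reproductive potential must "have a negative serum or urine pregnancy test performed within 48 hours before initiating the protocol-specified medication(s").
- The AMC baseline list (section 8.1.12.6) has: "Serum or urine pregnancy test for women of childbearing potential (within 7 days prior to Cycle 1 chemotherapy"). The same item sends the reader to 6.1.1, "under pregnancy and breastfeeding for guidelines on the use of pregnancy category D medications".
- AMC Appendix I has one pregnancy-test entry, at baseline, with footnote F: "To be performed within 7 days prior to Cycle 1, Day 1". French section 9.3 and the flow chart (code D-7) likewise show one baseline test, serum only, within 7 days.
- AMC section 3.1.10 adds: "Female participants must have a negative pregnancy test within 1 week of enrollment". French section 8.1 item 10 is the same.
- AMC section 3.0 says: "Participating sites must have documentation that each eligibility requirement is satisfied prior to participant enrollment". French section 8.0 agrees. Enrollment may be "no more than 1 week prior to the initiation of treatment", although "enrollment 1 day prior to or on the day of treatment is strongly encouraged" (AMC section 3.5; French section 11.1 matches).
- Testing during the study is left to local institutional policy (AMC 8.2.9; French 9.4 item 10).

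**Notification, French protocol only.** French 14.1.1 requires birth control during the study and for 6 months after treatment stops. Its next sentence asks the patient to report a pregnancy, her own or a partner's, that occurs during participation or within 30 days after treatment stops. The parallel sentence in AMC 6.1.1 says 6 months.

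**The concern.** The 48-hour test is stated as mandatory for a regimen containing two drugs that the protocol places in pregnancy category D, brentuximab vedotin and dacarbazine. Sites usually work from the schedule table. A site that follows the table alone can complete every listed procedure and still miss the mandatory window.

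On notification, the manufacturer's follow-up of a pregnancy to term depends on someone reporting it. If a French site reads the 30-day figure as the end of the post-treatment reporting period, a pregnancy in months 2 to 6 may go unreported, although contraception was still required then. The clause covers partners, so it concerns male participants as well as women.

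Both matters concern patient safety and the consistency of the documents.

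**Working it through.** The plan states no figure to reproduce. The check compares time windows.

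**1. Size of the test-window difference.**
- Schedule: 7 days x 24 h = 168 h before Cycle 1 (AMC 8.1.12.6 and Appendix I footnote F; French 9.3 and flow chart).
- Rule: 48 h (AMC 6.1.1; French 14.1.1).
- Difference: 168 - 48 = 120 h, or 5 days.
- The eligibility wording alone would allow 1 week before enrollment plus 1 week from enrollment to dosing, about 14 days. The baseline lists cap this at 7 days, so 120 h is the limit.

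**2. When the scheduled test cannot meet the rule.** Eligibility must be documented before enrollment, so the eligibility test is at least as old at dosing as the interval from enrollment to dosing. Call that interval h, with 0 <= h <= 168 hours.
- If h <= 48, one test can satisfy the eligibility criterion, the schedule and the 48-hour rule together.
- If h > 48, the eligibility test is already outside the 48-hour window at dosing, and only a second test can meet the rule. For example, with h = 96 the test is 96 to 168 hours old, which is 48 to 120 hours too early.
- Neither schedule lists that second test.

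The documents give no distribution of h, so the share of women affected cannot be computed. AMC Table 13-A targets 4 women among 51 participants. It does not give childbearing potential or the split between countries.

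**3. Size of the French notification gap.**
- 6 months = 365.25 / 2 = 182.6 days, and 182.6 - 30 = 152.6, about 153 days (days 31 to 183).
- If follow-up counts as participation, the first limb of the sentence covers this period and the gap is 0.
- If participation ends with treatment, the gap is about 153 days.

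**4. Scheduled contact inside that period.** French section 9.5 sets a visit 6 to 8 weeks after the last dose (days 42 to 56), then every 3 months. Adding 91 days gives days 133 to 147, or 126 to 154 with the 7-day tolerance. Two visits therefore fall within days 31 to 183 for patients who complete treatment. History and examination are done there, but no pregnancy test is listed. Early discontinuers have a visit within 1 month and are then followed for survival only (French 9.6), except that those stopping after CR or PR are also followed for recurrence (French 9.5 and synopsis).

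**The case against.** **On the test.** A test taken within 48 hours of dosing satisfies the rule, the baseline item and footnote F at once, and a stricter requirement placed elsewhere still binds. AMC 8.1.12.6 points to 6.1.1, so an AMC site that follows the whole item is led to the 48-hour rule. All of this stands. A reader might infer that the provisions contradict each other, and they do not. The pointer, however, speaks of guidance on category D drugs and does not mention a second test, and the Appendix I footnote lacks it. In the French protocol the pointer names section 13.1.1, while the text is in 14.1.1.

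A reader might also infer that no further pregnancy testing takes place. That is too strong. AMC 8.2.9 and French 9.4 item 10 provide for tests under local policy. They sit in a section that includes checks within 48 hours before or on Day 1 of each cycle, so a local policy could supply a test before the first dose. No fixed time is set, so it is not assured.

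**On notification.** A reader might infer that French 14.1.1 ends notification at 30 days. The sentence offers two alternatives, and the first covers the whole of participation. French section 7.0 defines the end of study by the last planned follow-up visit, which supports counting follow-up. French section 8.1 items 10a and 10b separately require women who become pregnant, and men who father a child, to report it while participating, with no 30-day limit. Birth defects must also be reported through CTEP-AERS (French 14.3.3). Against this, if the study in that paragraph includes five years of follow-up, neither the 30 days nor the 6 months adds anything, which suggests that the paragraph means the treatment phase. A birth-defect report also captures an outcome and not the pregnancy itself. The text remains open to both readings.

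**Conclusion.** Both points hold in limited form, and both are minor.

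1. In both protocols the schedule is looser than the mandatory rule by up to 120 hours. The two can be reconciled, but a woman enrolled more than 48 hours before dosing needs a test that neither schedule lists. This rests on the eligibility test preceding enrollment, as AMC 3.0 and French 8.0 require. The advice to enroll on the day before treatment or the day itself should make such cases uncommon.
2. In the French protocol only, the notification period after treatment does not match the contraception period in its own paragraph or the AMC text. The gap is 0 to about 153 days, depending on what participation means.

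The outdated cross-reference in French 9.3 is clerical.

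A reader might infer that many women would be dosed without a valid test, or that pregnancies would be missed in some number. The documents support neither: the target is 4 women, no expected number of pregnancies is given, pregnancy is an exclusion, and a negative test within 7 days and two contraceptive methods are required. There is no effect on PFS, the sample size or any planned analysis.

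**What to change.** 1. Keep the 7-day eligibility test. Shortening its window would leave women enrolled on days -7 to -3 with no scheduled eligibility test. Add one line to AMC 8.1.12.6 and Appendix I, and to French 9.3 and the flow chart: a pregnancy test within 48 hours before Cycle 1 Day 1, not needed if the eligibility test already falls in that window. Specify serum or urine in the AMC protocol, and serum in the French one to match French 9.3, the flow chart and exclusion criterion 2. Draw it with the CBC already required within 48 hours of Day 1 (AMC 8.2.5; French 9.4 item 6), whose result must be known before treatment.
2. In French 14.1.1, change the notification period after treatment from 30 days to 6 months.
3. In French 9.3, correct the reference from 13.1.1 to 14.1.1.

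The cost is one schedule line per protocol, one phrase and one section number. It means at most one repeat test per woman, so up to 4 at the Table 13-A target, at a time when blood is already due. It adds no test beyond what the 48-hour rule already demands.
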